#### 5.6. The need for the EndoNET trial

During the COVID-19 pandemic, and its multiple waves, large numbers of patients within the UK and worldwide were placed on "bridging" NET until theatre capacity became available, despite lack of level 1

© Copyright: The University of Oxford and Oxford University Hospitals NHS Foundation Trust 2022 Page 27 of 84

evidence. It is therefore important going forward to understand the significance, impact and effectiveness of a NET strategy, which continues to be used post-pandemic in secondary care UK hospitals.

If NET is shown to increase BCS rates (reducing mastectomy rates) and reduce burden of surgery (smaller volume resections, reduced re-excision rates and reduced axillary treatment) there would be significant benefit to both patients and to the NHS, including reduced quantity and extent of surgery, quicker recovery and progression to further adjuvant treatments, improved cosmesis, satisfaction, body image, self-esteem, sexuality and reduced anxiety and depression (8). These patient and health economic benefits are commensurate with the objectives of the national "getting it right first time" (GiRFT) initiative (60). The detrimental effects of mastectomy to HRQoL and body image persist regardless of age (20, 23, 24). Benefits to women of BCS include better HRQoL and a reduction in requirement for post-mastectomy reconstruction and its complications. For those treated by BCS, the benefits of NET potentially include reduction in excision volumes, fewer patients requiring for more complex BCS techniques and reduction in re-excision rates. Since ET is widely given and of low toxicity, benefit would be seen across the age spectrum. Improving cancer outcomes in the elderly is important (61) and as comorbidity and age increases, mastectomy is more likely, whilst reconstruction and chemotherapy (including as a neoadjuvant/downstaging option) is less frequently utilised (4).

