#### 6.2 Primary and secondary outcome measures

2	. To evaluate tumour response rates following NET 	2.	Response rates according to RECIST (USS, clinical, relative to baseline); MRI where used as part of local unit centre policy	2.	2-4 weeks, 3 and 5 months post- randomisation (NET arm)
3	
 
To compare invasive tumour size, histological grade and lymph node status (including number of involved nodes) in both arms
 
	3.	Tumour size, histological grade and lymph node status pre-surgery and final histology post-surgery	3.	Pre and post- operative
4		4.	Patient reported outcomes as measured by FACT-B (with ES and +4), Breast-Q, Hopwood Body Image Scale and EQ-5D-5L	4.	Baseline, 6 weeks or post-operative, 5, 7, and 15 months post- randomisation 
5		5.	Pre-operative Endocrine Prognostic Index (PEPI) score	5.	Baseline sample, 2-4 week sample and post- operative sample
6	To compare post-surgical complications and AI side effects in both arms 	6.	Post-surgical complications, side effects; delays to commencement of subsequent treatment	6.	2-4 and 6 weeks, 3 months, 5, 7, 12 and 15 months post- randomisation
7		7.	Treatment Compliance and rates of cross-over	7.	2-4 weeks, 5 months and 15 months post- randomisation.
8	. To evaluate the prognostic significance of Ki67 	8.	Ki67 % in tumour cells, % reduction in Ki67 from baseline to biopsy or surgery	8.	Baseline (both arms) and after 2- 4 weeks of AI (in both arms) and at surgery (in comparator arm);

9. To assess the surgical and locoregional management of the breast 	9. Rates of re-excision and further surgery after BCS; specimen weight after BCS; requirement for advanced BCS (therapeutic mammoplasty and local perforator flaps), rate of reconstruction	9. Baseline, post- operative, 15 months post- randomisation
10. To assess the surgical and locoregional management of the axilla 	postmastectomy, breast radiotherapy 10. Rates of sentinel node biopsy, axillary clearance, axillary radiotherapy	10. Baseline, post- operative, 15 months post- randomisation
11. To compare rates of local and distant recurrence 	11. Rates of local and distant recurrence	
 
11. 15 months post- randomisation, and periodically for long term follow up 
 

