# 7. TRIAL DESIGN

#### 7.1 Type of trial

This is a prospective, phase III, parallel group, multicentre, superiority randomised controlled trial (RCT).

EndoNET\_Protocol\_V4.0\_21Aug2024

© Copyright: The University of Oxford and Oxford University Hospitals NHS Foundation Trust 2022 Page 33 of 84

We will recruit a maximum of 1,060 (for 90% power) with a minimum of 792 (for 80% power) postmenopausal women with strongly ER+ invasive breast cancer who are not planned or have not started chemotherapy or anti-HER-2 therapy from secondary care UK hospital breast units. They will be randomised 1:1 to undergo 6 (+/- 1) months of NET followed by surgery and adjuvant ET or to surgery within 2-4 weeks (up to 8 weeks permitted for trial purposes) followed by adjuvant ET. Flexibility in the scheduling of a month either side of the target of 6 months in the NET arm and up to 8 weeks in the comparator arm is designed to accommodate the practicalities of the logistics of surgical planning. It was also highlighted an important factor by patients at the PPI meeting and is consistent with levels of pragmatic flexibility. Both arms receive the same treatment modalities (surgery, ET, and radiotherapy where indicated), but the sequencing of surgery will differ, with both arms starting ET at randomisation, with 6 months of the course of ET delivered prior to surgery in the NET arm. The primary outcome measure is the proportion of women who have BCS at 15 months. If aromatase inhibitor endocrine therapy has already been started following the current breast cancer diagnosis as part of routine care prior to joining the trial, then this is permitted, as long as trial entry is within 14 days of starting treatment.

The study duration is 69 months including, 6 months setup, 42 months recruitment, 15 months follow-up and 6 months data analysis and final reporting of results.

[figure not shown]
A formal stop/go review took place on 31st December 2023 to ensure 12 sites opened and 150 participants were randomised. The Funder granted a continuation of recruitment with a second review point in December 2024. Data from the internal pilot will be included in the final analysis.

EndoNET\_Protocol\_V4.0\_21Aug2024

© Copyright: The University of Oxford and Oxford University Hospitals NHS Foundation Trust 2022 Page 34 of 84

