## 9.6. Randomisation (Main Trial)

We will randomise eligible patients using the centralised validated computer randomisation program through a secure (encrypted) web-based service, RRAMP (https://rramp.octru.ox.ac.uk), provided by the Oxford Clinical Trials Research Unit (OCTRU), accessed via the study's REDCap instance, with a minimisation algorithm to ensure balanced allocation across treatment arms, stratified in a 1:1 ratio to either NET followed by standard of care or standard of care using:

- Age group (<60, 60-70, 70+ years);
- Nodal status (N0 vs N1 or N2);
- Recruiting centre, and
- Surgical indication at baseline (BCS vs mastectomy)

To ensure the unpredictability of treatment allocation the minimisation algorithm will include a probabilistic element and a small number of participants randomised by simple randomisation. Stratification by centre will help to ensure that any centre-effect will be equally distributed in the trial arms and enable practical issues associated with the active intervention to be overcome. In the unlikely event that the randomisation system is down for any reason, if delays in randomisation occur to such an extent that they impact treatment planning felt to affect the prognosis of the participant, then they will be withdrawn and returned to the usual standard of care pathway if deemed necessary by the treating clinician. For participants who do not wish to or who are unable to comply with their randomisation outcome (according to the investigator and/or clinical team), they will continue to participate in the study but will be analysed on an intention to treat basis.

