Secondary endpoints, measured in both treatment groups, will be analysed comparatively as far as practically possible. Statistical methods used for comparison will depend on the outcome type and full details will be included in the SAP. QoL will be compared using a mixed effects linear regression model. The model will include treatment, baseline score and clinical stratification factors as fixed effects, centre will be included as a random effect. When QoL is assessed at additional time points between baseline and 15 months, time-by-treatment interactions will be incorporated as fixed effects and patient as a random effect. Mean scores and standard deviations will be plotted over time for visual representation. The predictive ability of Ki67 will be explored using logistic regression models. Time-to-event endpoints will be analysed using Kaplan-Meier curves, log rank tests, and Cox proportional hazards models or, in the presence of competing risks, by using cumulative incidence plots and Fine and Gray survival regression models. Continuous clinical endpoints will be compared using a two-group t-test and the difference in means will be presented with a 95% confidence interval. Binary clinical endpoints will be compared using a chi-squared test and the effect estimate reported in terms of the relative risk and 95% confidence interval. Ordinal clinical endpoints will be compared using a chi-squared test for trend. Multilevel regression models, with adjustment for stratification factors in line with the primary endpoint analyses, will be applied to secondary endpoints where it is both practical to do so and there are sufficient events to support this approach.

The primary analysis is planned in the final six months of the study period, at which point all participants will have completed at least 15 months of follow-up.

It is anticipated that all statistical analysis will be undertaken using Stata (StataCorp LP, www.stata.com) or other well validated statistical package.

\* **Note:** From Protocol 4.0, FACT-B +4/ES will no longer be collected at 7 and 12 months (see Appendix 1). Data collected on patients up until this timepoint will be reported descriptively and will not be included in formal comparisons due to low numbers in comparison with the overall sample size. The SAP will provide further detail.

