## 12.3 Sample Size Determination

We aim to recruit a maximum of 1060 patients (for 90% power, 530 per arm), with a minimum of 792 (for 80% power, 396 per arm) women from at least 30 NHS centres. UK-based registry data indicates that ~45% of women with tumours >2cm undergo mastectomy; based on discussions with patient representatives and confirmed at the NCRI Dragons Den, we consider a reduction of 10% (i.e. mastectomy rate reduced from 45% to 35% resulting in BCS rate increase from 55% to 65%) to be clinically meaningful to patients and lead to a change in clinical practice.

EndoNET\_Protocol\_V4.0\_21Aug2024

© Copyright: The University of Oxford and Oxford University Hospitals NHS Foundation Trust 2022 Page 63 of 84

The sample size of 1060, and 792, would allow us to detect this difference with 90% and 80% power respectively at a two-sided 5% significance level allowing for a cross-over and attrition at 15 months up to 5%.5% is based on loss to follow up experienced for the clinical endpoints in the iBra study.

80% power is considered to be sufficiently robust and in line with other similar and recent trials (104, 105). However, if recruitment to 1060 (for 90% power) seems achievable, given the observed recruitment trajectory, then the DSMC and TSC will be contacted to consider continuation of recruitment to 1060 patients.

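### Re-excision and specimen weight are defined after BCS, a group that NET is expected to change, and the default tests do not allow for it

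*Protocol*

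**What the plan says.** Outcome 9 in the protocol's Section 6.2 (repeated in the Synopsis) covers "Rates of re-excision and further surgery after BCS; specimen weight after BCS; requirement for advanced BCS", followed by the rate of reconstruction after mastectomy. The restriction to women who had BCS is explicit for re-excision or further surgery and for specimen weight. For advanced BCS the denominator is not stated, although Section 5.6 places that benefit in the same group: "For those treated by BCS, the benefits of NET potentially include reduction in excision volumes, fewer patients requiring for more complex BCS techniques".

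Section 12.2 sets the default analysis: "Binary clinical endpoints will be compared using a chi-squared test and the effect estimate reported in terms of the relative risk". Continuous clinical endpoints get a two-group t-test. Multilevel models that adjust for the stratification factors are to be used for secondary endpoints only where this is practical and there are enough events. One of those factors, in Section 9.6, is "Surgical indication at baseline (BCS vs mastectomy"). Section 12.6 treats outcomes collected in both arms as significant at p<0.05.

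The design assumption in Section 12.3 is "mastectomy rate reduced from 45% to 35% resulting in BCS rate increase from 55% to 65"%.

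**The concern.** The BCS group and the mastectomy group form after randomisation, and the trial's hypothesis is that NET moves women from the second to the first. If so, the NET BCS group contains women who would have had BCS in either arm plus women converted from mastectomy. The control BCS group contains only the former. A chi-squared test or t-test between the two groups is then not a comparison of like with like. The mirror problem applies to reconstruction after mastectomy, because the converts are missing from the NET mastectomy group.

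If converts have more re-excision or heavier specimens than other BCS patients, a real benefit of NET would look smaller than it is, vanish or change sign. If they have less, the benefit would be overstated. The end of the general background in Section 5 names a lower re-excision rate among the things the study is designed to determine, so a misleading result would bear on a stated purpose of the trial.

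**Working it through.** **1. The plan's own sample size.** Inputs from Sections 7.1 and 12.3: 55% v 65%, 1:1 allocation, "90% and 80% power respectively at a two-sided 5% significance level", "allowing for a cross-over and attrition at 15 months up to 5"%. Two-proportion formula with pooled variance and no continuity correction, then division by 0.95:
- 80% power: 376 per arm; 376/0.95 = 395.8, so 396 per arm and 792 in total.
- 90% power: 503 per arm; 503/0.95 = 529.5, so 530 per arm and 1060 in total.

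Both stated figures are reproduced and are not in question.

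**2. Share of women without a counterpart.** Assume that no woman loses BCS because of NET.
- NET BCS group: (0.65 − 0.55)/0.65 = 0.10/0.65 = 15.4% are converts.
- Control mastectomy group: 0.10/0.45 = 22.2% are women who would have been converted under NET.
- After 5% attrition, the BCS groups are about 207 control and 245 NET at N=792 (376.2 × 0.55 and × 0.65), or 277 and 327 at N=1060.

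**3. What the after-BCS comparison shows.** Let *a* be the NET re-excision rate in women who would have BCS in either arm, and *c* the rate in converts. Control is set at 20%; Section 5 says over 20% in the UK. Then:

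observed NET rate = (0.55*a* + 0.10*c*)/0.65

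The true fall is fully hidden when *c* = (0.65 × 0.20 − 0.55*a*)/0.10:

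| True rate *a* (control 20%) | Converts' rate at which the fall is hidden |
|---|---|
| 19% | 25.5% |
| 18% | (0.130 − 0.099)/0.10 = 31% |
| 17% | 36.5% |
| 16% | (0.130 − 0.088)/0.10 = 42% |
| 15% | 47.5% |
| 10% | 75% |

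Two examples with assumed convert rates:
- *a* = 16%, *c* = 40%: (0.088 + 0.040)/0.65 = 19.7%, against 20%.
- *a* = 18%, *c* = 35%: (0.099 + 0.035)/0.65 = 20.6%, against 20%.

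Short of reversal, the effect is diluted. With *a* = 15% and *c* = 35% the observed rate is 18.1%, a relative risk of 0.90 instead of 0.75. Power falls from 29% to 7.5% at N=792, and from 37% to 9% at N=1060.

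Specimen weight follows the same algebra. A true 10% reduction is hidden if converts average (0.65 − 0.55 × 0.90)/0.10 = 1.55 times the control mean.

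**4. What adjustment would do.** Take the first example and suppose all converts come from the mastectomy-indicated stratum and no such woman has BCS in control. The filled cells are control/BCS-indicated 20%, NET/BCS-indicated 16% and NET/mastectomy-indicated 40%. A model with treatment and indication terms fits these three cells exactly, and its treatment term is 16% v 20%. Adjustment therefore recovers the true effect here.

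**5. All-randomised alternatives.** Counting re-operation over everyone randomised, with one operation per mastectomy patient:
- Control: 0.55 × 0.20 = 11.0%.
- NET: 12.8% (first example) or 13.4% (second).

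This rises simply because more women have BCS. A composite of mastectomy or re-operation gives 0.45 + 0.11 = 56.0% in control, against 0.35 + 0.128 = 47.8% or 0.35 + 0.134 = 48.4% in NET.

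**6. Precision in the BCS-indicated stratum.** If 55% of women are BCS-indicated (an assumption), power for 20% v 15% is about 27% at N=792 and 34% at N=1060.

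**The case against.** The strongest reply is that the protocol lists outcome measures, not analysis sets. Objective 9 is worded as an assessment, whereas several others are worded as comparisons. Section 12.4 makes intention to treat the principal analysis, and Section 12.2 leaves details to the SAP, which is not available here. Section 12.2 also foresees adjusted models, and step 4 shows that adjustment for baseline surgical indication works in the simple case. With BCS groups of about 207 and 245 and a rate near 20%, some 90 re-excisions are expected, so the model is probably feasible.

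Much of this stands. A reader might infer that adjustment cannot help; on the illustrated pattern that is wrong. A reader might also infer that the analysis is bound to count against NET. The documents do not support that. They give no re-excision rate or specimen weight for converts and do not say that converts fare worse, and converts' tumours will have shrunk by surgery. The reversal of 0.6 points (20.6% v 20%) is small beside a standard error of about 3.8 points at N=792, and a large true effect (20% to 10%) would need a convert rate above 75% to be reversed.

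What does not fall away is that the conditional definition and the unadjusted default test are both written into the protocol, while the adjustment that would help is optional.

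**Conclusion.** The point holds as a weakness in a secondary outcome. Comparing re-excision, further surgery and specimen weight after BCS, or reconstruction after mastectomy, with an unadjusted test is not a randomised comparison if NET works as planned, since about 15% of the NET BCS group would have no control counterpart. The size and direction of the bias depend on how converts differ, which the documents do not tell us. The thresholds above (31% to hide a fall to 18%, 42% to hide a fall to 16%) rest on control re-excision of 20%, the planned 55% and 65%, and no woman losing BCS through NET.

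A reader might go further and take this as undermining the main result, or as covering advanced BCS on the same explicit footing. Neither follows: the primary outcome and the sample size are unaffected, and the BCS-only denominator for advanced BCS is an inference from Section 5.6. Nor do the documents give re-excision and excision volume any fixed share of the claimed benefit; Section 5 presents them as additional to the BCS rate.

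**What to change.** 1. For re-excision or further surgery and for advanced BCS, make the main comparison among all women randomised in the baseline BCS-indicated stratum, in their randomised arms, and report an estimate with a 95% confidence interval. State how a woman in this stratum whose first operation is a mastectomy is counted.
2. Do the same for specimen weight where it is recorded. The protocol names specimen weight only after BCS, so mastectomy weight may not be collected.
3. Require any pooled after-BCS model to adjust for baseline surgical indication, without the practicality condition.
4. Present unadjusted after-BCS and post-mastectomy rates as descriptive only.
5. If an all-randomised measure of surgical burden is added, use the composite of mastectomy or re-operation. Re-operation or number of operations alone would count each extra BCS against NET.

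The cost is wording in the outcome table, Section 12.2 and the SAP. Baseline indication is already a minimisation factor, and Section 9.10 has surgery recorded in detail on the CRFs. The price is lower precision in the stratum (step 6), which is why an estimate with its interval should carry the result rather than a significance test.

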# 7. TRIAL DESIGN

#### 7.1 Type of trial

This is a prospective, phase III, parallel group, multicentre, superiority randomised controlled trial (RCT).

EndoNET\_Protocol\_V4.0\_21Aug2024

© Copyright: The University of Oxford and Oxford University Hospitals NHS Foundation Trust 2022 Page 33 of 84

We will recruit a maximum of 1,060 (for 90% power) with a minimum of 792 (for 80% power) postmenopausal women with strongly ER+ invasive breast cancer who are not planned or have not started chemotherapy or anti-HER-2 therapy from secondary care UK hospital breast units. They will be randomised 1:1 to undergo 6 (+/- 1) months of NET followed by surgery and adjuvant ET or to surgery within 2-4 weeks (up to 8 weeks permitted for trial purposes) followed by adjuvant ET. Flexibility in the scheduling of a month either side of the target of 6 months in the NET arm and up to 8 weeks in the comparator arm is designed to accommodate the practicalities of the logistics of surgical planning. It was also highlighted an important factor by patients at the PPI meeting and is consistent with levels of pragmatic flexibility. Both arms receive the same treatment modalities (surgery, ET, and radiotherapy where indicated), but the sequencing of surgery will differ, with both arms starting ET at randomisation, with 6 months of the course of ET delivered prior to surgery in the NET arm. The primary outcome measure is the proportion of women who have BCS at 15 months. If aromatase inhibitor endocrine therapy has already been started following the current breast cancer diagnosis as part of routine care prior to joining the trial, then this is permitted, as long as trial entry is within 14 days of starting treatment.

The study duration is 69 months including, 6 months setup, 42 months recruitment, 15 months follow-up and 6 months data analysis and final reporting of results.

[figure not shown]
A formal stop/go review took place on 31st December 2023 to ensure 12 sites opened and 150 participants were randomised. The Funder granted a continuation of recruitment with a second review point in December 2024. Data from the internal pilot will be included in the final analysis.

EndoNET\_Protocol\_V4.0\_21Aug2024

© Copyright: The University of Oxford and Oxford University Hospitals NHS Foundation Trust 2022 Page 34 of 84

## 7.2 Trial Schema (Main Trial)

Patient Related Outcome Measures (PROMs) will assess the participant's health status or HRQoL at individual time points and will be collected through questionnaires. PROMs include FACT-B (+4/ES), Breast-Q, BIS, EQ-5D-5L, Health Care Use Questionnaire and Compliance to ET/NET (MARS-5).

**Figure 1.** Left panel: Study schema. All participants should commence pre-surgical aromatase inhibitor endocrine therapy at randomisation if not already started as part of routine care; in comparator arm surgery at 2-4 weeks (within NHS 31-day target, although up to 8 weeks permitted for trial purposes) and in NET arm surgery at 6 months +/- 1 month. Additional core biopsy (Bx) and marker clip insertion at 2-4 weeks in NET arm. Right panel: All study measurement timepoints with corresponding clinical care visits for the two arms demonstrating study design to ensure comparability between arms and correspondence between timepoints and clinical pathway. Items marked \* will be conducted remotely: PROMs either electronically or by posted letter (including by telephone in some circumstances) and outpatient appointment (OPA) by telephone.

